#### Additional Analyses

We will report overall frequency (adding together all the adverse events reported) of adverse events by study arm, followed by the frequency of all types of adverse events by study arm. We will also report the total number of adverse events by severity and average duration, overall and by arm. We will also examine the frequency and percentage of school staff reporting adverse events (which will be counted once only for a given participant). We will also calculate adverse events by school level. We will report study arm-specific percentages of schools that had staff who reported any adverse event and by each type of adverse event.

Study arms will be compared on baseline characteristics (e.g., demographics) using descriptive statistics. We will test for differences in potential confounders between intervention and control arms using baseline staffand school-level data with Rao-Scott chi-square tests for categorical variables and linear mixed models (with a random effect for school) for continuous variables (models adjusting for the clustering of staff within schools).

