#### PLANTS Pilot Trial Version 1.0 Protocol STUDY21080178 2024.04.05 **OBJECTIVES ENDPOINTS** JUSTIFICATION FOR ENDPOINTS To assess PLANTS -PLANTS participation rate These measures assess school implementation -PLANTS completion rate staff's implementation and uptake of -Participation rate in live Zoom events the PLANTS intervention. To assess trial -Participation rate These measures assess the success implementation -Attrition rate of the pilot trial in reaching an -Intervention demand adequate number of school staff. To determine the -Parent backlash Although we anticipate the incidence safety of PLANTS -Social media backlash of these adverse events to be low. they are the most common and could -School board backlash be most harmful to school staff. -Suspension or removal from employment -Censorship of LGBTQ+ literature/history/stories or removal of books with LGBTQ+ representation from school libraries.

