# 4 STUDY DESIGN

# 4.1 Overall Design

This is a two-armed cluster-randomized controlled pilot trial of the PLANTS intervention versus an active control group, EMAILS (E-learning to Maximize Academic Inclusion of LGBTQ+ Students). The single study site is the University of Pittsburgh. The primary objective is to assess the acceptability, usability, appropriateness, and feasibility of the PLANTS intervention. We hypothesize that high school staff will rate the PLANTS intervention as having high acceptability, usability, appropriateness, and feasibility in the follow-up survey.

The secondary objectives are to examine the extent to which the PLANTS course and trial successfully implemented and safe for high school staff and schools. We will also evaluate the extent to which, among high school staff participants in the PLANTS arm, they report pre-post improvements in active-empathic listening, self-efficacy for supporting, affirming, and protecting sexual and gender minority youths, and positive bystander intervention behaviors for bullying. We will also assess the extent to which, among high school staff, the PLANTS intervention is more efficacious in improving active-empathic listening, self-efficacy for supporting, and positive bystander intervention behaviors for bullying than an email intervention of publicly available resources. We hypothesize that participants in PLANTS will report greater active-empathic listening, greater self-efficacy for supporting, affirming, and protecting SGMY, and greater positive bystander intervention behaviors in the active control arm.

We will randomize schools in an equal 1:1 ratio, stratified by large versus small schools, into intervention or active control conditions. We will use block randomization with block sizes of 2, which will be stratified by large schools versus not, where large is ≥1000 students. We use block size of 2 because there are only 4 schools in this pilot trial. [name] (PI) will use Stata (ralloc command) to generate the randomization list, which will be entered into REDCap using the randomization module. Because this is a cluster randomized trial, we will randomize schools after they are determined to have met all the eligibility requirements and they officially enroll in the study. Upon school enrollment, a research assistant will be responsible for entering the school into the REDCap database and hitting the "randomize" button. Randomization will occur prior to school staff

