#### 9.2 Sample Size Determination

#### Primary Endpoints

To adequately evaluate the primary endpoints, we need precise estimates of acceptability, appropriateness, and feasibility. We calculated our sample size based on our primary outcomes, a 5% error rate, and best practices for feasibility studies. The median number of teachers at each MetroWest Region high school is n=86. With 4 schools in our sample, we anticipate inviting a total  $\geq$ 344 school staff to participate in the pilot study. Assuming 50% agree to participate, 50% of participants are in the PLANTS study arm, and 75% of PLANTS participants complete the follow-up survey (reduced n=65), we can estimate 95% CI widths  $\leq$ 0.33 for AIM, IAM, and (based on the largest upper CI limit of the AIM, IAM, and FIM standard deviations) and  $\leq$ 10.1 for SUS. Such precision levels are sufficient.

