# 9.4.4 Safety Analyses

Hypothesis: High school staff in the PLANTS arm will have low adverse event prevalence (≤20% of PLANTS participants will report adverse events).

We will estimate the prevalence of adverse events by calculating the percentage and 95% confidence interval of school staff that reported adverse events experienced any time after PLANTS deployment and use.

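### The safety outputs specified by arm are raw event sums and an any-report school percentage; both rise with the number of staff who respond, so they cannot separate event risk from response volume

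*Combined protocol and SAP*

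**What the plan says.** Section 9.4.4 (Safety Analyses) has two layers.

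- **Main estimate.** "We will estimate the prevalence of adverse events by calculating the percentage and 95% confidence interval of school staff that reported adverse events", counted from PLANTS deployment onward. The linked hypothesis is that "≤20% of PLANTS participants will report adverse events". Both concern the PLANTS arm.
- **Additional Analyses.** The first output is a sum: "We will report overall frequency (adding together all the adverse events reported) of adverse events by study arm". Counts by type follow, also by arm, then totals by severity with average duration, overall and by arm. The person-level item reads "We will also examine the frequency and percentage of school staff reporting adverse events (which will be counted once only for a given participant"; unlike its neighbours, it does not mention study arm, event type or school. One short sentence says that events will also be calculated at school level, without saying how. The last item is "We will report study arm-specific percentages of schools that had staff who reported any adverse event and by each type of adverse event".

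Section 4.1 says "there are only 4 schools in this pilot trial" and allocates them 1:1. Section 9.2 gives the size: "The median number of teachers at each MetroWest Region high school is n=86".

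**The concern.** A sum of events and a flag for at least one report share a property: with individual risk held fixed, each rises with the number of people who could report. Schools are randomised, not staff, and staff enrol after randomisation, so the number answering can differ between schools and between arms. Sections 4.1 and 6.3 themselves warn that the unblinded design may cause attrition bias and bias in reporting adverse events.

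A reader who sets the two arms side by side would therefore see a mixture of event risk and response volume. Section 2.1 says the pilot is to inform a fully powered trial, and these are the tables from which its designers would judge whether PLANTS staff met more backlash than EMAILS staff.

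The sums have a further weakness. Several solicited events in Section 8.2 happen to a school rather than a person, such as school board backlash or removal of books. Many colleagues can report one incident, and no rule removes duplicates across staff. The count-once rule applies only to the person-level figure.

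**Working it through.** **1. The plan's own safety precision figure.** Section 9.2 (Secondary Endpoints) gives a 95% CI width of no more than 0.21 for the proportion of PLANTS staff reporting events, at n=86. The Wald width at p=0.5 is 2 × 1.96 × √(0.25/86) = 0.211, so the figure is reproduced. It belongs to the person-level estimate. No precision is stated for the school percentage or for the sums.

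**2. Staff per school.** Section 9.2: 4 × 86 = 344 invited; × 0.5 = 172 consenting; × 0.5 = 86 in PLANTS; × 0.75 = 64.5, stated as 65, at follow-up. Over two schools that is about 43 enrolled or 32 responding per school. Equal school sizes are assumed.

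**3. Possible values.** Four schools at 1:1 give two per arm, so the school percentage is 0, 50 or 100%.

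**4. Probability that a school is flagged.** With individual rate p, m staff and independent reports, P = 1 − (1 − p)^m. Both schools in an arm: P². All four, with the same p in both arms: P⁴. The documents give only the 20% ceiling for PLANTS; the other rates are assumed to show the range.

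| p | P, m=32 | P, m=43 | both in arm, m=32 | all four, m=32 |
|---|---|---|---|---|
| 20% | 0.999 | 1.000 | 0.998 | 0.997 |
| 10% | 0.966 | 0.989 | 0.933 | 0.870 |
| 5% | 0.806 | 0.890 | 0.650 | 0.423 |
| 2% | 0.476 | 0.581 | 0.227 | 0.051 |
| 1% | 0.275 | 0.351 | 0.076 | 0.006 |

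**5. Where it saturates.** A 95% chance that all four schools are flagged needs P = 0.95^(1/4) = 0.987. Solving p = 1 − (1 − 0.987)^(1/m), with 0.987 unrounded, gives 12.7% at m=32 and 9.6% at m=43.

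**6. Clustering within schools.** Under a beta-binomial model with an assumed intraclass correlation of 0.10 and m=32, P falls from 0.999 to 0.949 at p=20%, from 0.966 to 0.764 at 10%, and from 0.806 to 0.509 at 5%.

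**7. Dependence on respondents at fixed risk** (assumed respondent numbers).

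- p=5%: P is 0.64, 0.81 and 0.95 for 20, 32 and 60 respondents. Expected reporters are 1.0, 1.6 and 3.0.
- p=3%: 1 − 0.97^20 = 0.456 and 1 − 0.97^60 = 0.839.
- Raw sums: arms with 80 and 50 respondents at equal risk differ in expected total by 80/50 = 1.6, that is 60% more events in the larger arm.

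**The case against.** **Saturation.** A reader might infer that the school percentage will be about 100% in both arms. The documents do not support that. The 20% figure is a ceiling, it covers PLANTS only, no EMAILS rate is given, and the endpoint table in Section 3 anticipates low incidence. At p=5% and m=32, an arm has 0, 1 or 2 flagged schools with probability 0.04, 0.31 and 0.65, so the two arms' percentages differ about 48% of the time (1 − 0.04² − 0.31² − 0.65², with unrounded probabilities). Rare types do not saturate: at an assumed 1 to 2%, a school is flagged with probability 0.28 to 0.58.

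**A person denominator already exists.** This stands for the main estimate, which is a percentage with a confidence interval. The additional person-level percentage is also planned; what it lacks is the words by arm and by type. The challenged outputs are descriptive, and the plan sets no comparative safety test, so failing to prove excess harm over EMAILS is not a defect in itself. The sentence on events at school level may be meant as a per-school table, but it does not say so.

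**An any-report flag suits school-wide incidents.** This also stands. The objective covers schools as well as staff. For a board dispute, whether anyone at the school reported it is a sensible question, whereas events per 100 staff would count one incident repeatedly. Dropping the flag would go too far.

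**The denominator.** Section 8.3.4 also captures events through Live Zoom Events, interviews and direct contact. Survey responders are the wrong base for those, and Live Zoom Events exist only in the PLANTS arm.

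**Respondent numbers.** The examples of 20 versus 60 and 80 versus 50 are assumptions. Section 9.2 plans for equal arms, and stratification by school size limits imbalance. Neither ensures equal response.

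**Anonymity.** Four schools by event type, including suspension or removal from employment, could identify individuals; Section 9.4.8 requires protection against that.

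**Conclusion.** The concern holds in a limited form. As written, the by-arm safety tables consist of sums and an any-report school percentage, and neither separates event risk from response volume. The school percentage takes three values per arm. It is nearly uninformative if the any-event rate is about 10 to 13% or more in both arms; below that, and for rare types, it can vary but still moves with the number of staff who answer.

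The main PLANTS estimate against the 20% benchmark is untouched, so this is a reporting weakness in secondary descriptive tables. It is worth correcting because the remedy is nearly free.

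The figures assume equal school sizes, the same rate in both arms and independent reports; clustering lowers the saturation probabilities. They also assume two schools per arm, which block size 2 within size strata guarantees only if each stratum holds an even number of schools. That the sums and the flag rise with respondents does not depend on the particular rates assumed.

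**What to change.** In the Additional Analyses of Section 9.4.4:

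1. State the percentage of staff with at least one event, each person counted once, by arm and by event type, with its denominator.
2. Show events per 100 staff beside the raw sums, and keep the sums.
3. Add one row for each of the four schools: staff at risk or responding, number reporting, and percentage.
4. Match the denominator to the route of capture: survey responders for events solicited in surveys. List events from Live Zoom Events, interviews or other contact separately.
5. Keep the any-report school flag as a secondary description for school-wide incidents, shown as a number out of 2 schools rather than a percentage.
6. Suppress or pool small cells by type, in line with Section 9.4.8.

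The cost is SAP wording and slightly larger tables. No new data are needed.

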# 9.4.6 Planned Interim Analyses

N/A

# 9.4.7 Sub-Group Analyses

Primary endpoints will be analyzed based on gender, sexual identity, race/ethnicity, intrinsic religiosity, religious attendance, religious activity, and role in school. Average score differences will be estimated using mixed models with demographic characteristics as predictors and the primary endpoints as outcomes, adjusting for school clustering.

Secondary endpoints of PLANTS efficacy will be analyzed based on gender, sexual identity, race/ethnicity, intrinsic religiosity, religious attendance, religious activity, and role in school (i.e., effect modifiers). Multivariable models will contain the 3-way interaction term, all 2-way interaction terms, main effects of time, study arm, the potential effect modifier, and any variables that meaningfully differ between study arms at baseline. We will conduct both intent-to-treat and per-protocol analyses. A significant 3-way interaction suggests the presence of intervention effect heterogeneity. Following the approach of Kraemer to focus on effect size derivation, we will use Stata's postestimation "margins" command to probe the 3-way interaction terms to provide simpler meaningful results.

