# **3 OBJECTIVES AND ENDPOINTS**

OBJECTIVES	ENDPOINTS	JUSTIFICATION FOR ENDPOINTS
Primary		
To evaluate the acceptability, usability, appropriateness, and feasibility of PLANTS	In the follow-up survey, school staff will complete the following survey measures: - Acceptability of Intervention Measure - System Usability Scale - Intervention Appropriateness Measure - Feasibility of Intervention Measure	We use validated scales that assess high school staff's perceptions of the intervention's tolerability, user friendliness, fit, relevance, and successful execution.
Secondary		
To test the efficacy of PLANTS intervention for improving SGMY behaviors among high school staff	-Active empathic listening -Self-efficacy for supporting, affirming, and protecting SGMY -Self-efficacy of PLANTS change objectives -Positive bystander intervention behaviors	PLANTS is specifically designed to target these behavioral outcomes.

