# PLANTS Pilot Trial

calculate the mean score for the total scale. Prior research shows Cronbach's alphas range from 0.88-0.90.

- **3. Self-efficacy for working with SGMY**: We assess participants' perceived abilities for working with LGBTQ high school students using 9 items adapted from the Gay Affirmative Practice Scale. Originally for social work practitioners, we adapted this scale by using school-oriented words instead of therapy-oriented words (e.g., "students" instead of "clients"). Example items included "I am able to help LGBTQ students develop positive identities as LGBTQ individuals" and "I am able to challenge misinformation about LGBTQ individuals in the classroom." Response options included a five-point Likert scale ranging from "strongly agree" to "strongly disagree." We will calculate the mean score for the scale. In a prior study, Cronbach's alpha = 0.90.
- **4. Bystander intervention behaviors for bullying:** Two multidimensional scales (Teacher Bystander Intervention Model in Traditional Bullying and Cyberbullying) measuring 5 subscales of bystander behaviors each: noticing the event (3 items), interpreting event as an emergency (3 items); accepting responsibility to help (3 items); knowing how to help (3 items); and implementing intervention decision (4 items). The psychometric properties of these subscales are good (Cronbach's alphas range=0.57-0.88). We will calculate average subscale scores. We will add items to these scales to specify SGMY-related bullying events using language from GLSEN's National School Climate Survey.
- 5. Self-efficacy of PLANTS' change objectives: Given the limited research contained validated scales of behavior change pertaining to LGBTQ inclusive practices in schools, our team has developed items pertaining directly to the self-efficacy change objectives in PLANTS. Each question will be asked on a scale of 1-5 (1: not at all certain; 2: slightly certain; 3: moderately certain; 4: very certain; 5: extremely certain).
  - a. **Provide interpersonal support and affirmation.** How certain are you that you are able to successfully: ask students about their chosen names? Use students' chosen names? Ask students about their pronouns? Use students' pronouns? use "reinforcing language" with students? "affirmations" with students? share about your personal connections to the LGBTQ+ community with your LGBTQ+ students?

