# Secondary Endpoints

We anticipate inviting at least 344 school staff to participate in the pilot study, and assuming 5% type I error rate, we will be able to estimate a 95% confidence interval width of no more than 0.11 for the participation rate. Assuming a participation rate of 50% (n=172), we will be able to estimate a 95% confidence interval width of no more than 0.15 for the attrition rate. Assuming half of the consenting participants are in the intervention arm (n=86), we will be able to estimate 95% confidence interval widths of no more than 0.21 for the proportion of school staff who adhere to the PLANTS intervention and for the proportion of school staff who report adverse events.

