# 9.4 Statistical Analyses

# 9.4.1 General Approach

With the ITT Analysis Population, we will calculate baseline descriptive statistics by study arm using means and standard deviations for continuous variables, and frequencies and percentages for categorical variables. We will test for differences in potential confounders between intervention and control arms using baseline staffand school-level data with Rao-Scott chi-square tests for categorical variables and linear mixed models (with a random effect for school) for continuous variables (models adjusting for the clustering of staff within schools). Secondary analyses will adjust for imbalances between arms. For previously validated scales, we will report

internal consistency via Cronbach's alpha for continuous scales. For newly created items, we will conduct exploratory factor analyses to examine the dimensions of our outcomes as well as internal consistency using baseline surveys. We will use the most recent version of Stata. All tests are two-tailed and  $\alpha$ =0.05. Given the small sample size and pilot nature of these analyses, we will not perform any corrections for multiple tests.

Regarding qualitative analyses, we will transcribe, de-identify, and quality check all data. We will perform qualitative analyses in Dedoose. We will use CFIR as a guiding framework. Two qualitative coders will independently read interviews and compare coding until they agree they are on the same page. Once the coders, we will create a final codebook with definitions, rules, and examples for each code. Two coders will then recode all data using the final codes. We will calculate inter-rater reliability (i.e., Kappa statistic) to examine code application between coders. Coders will discuss any discrepancies until they reach agreement; [name] will resolve disagreements. We will use either a qualitative descriptive coding approach (wherein we describe and count the number of code applications) or axial coding (wherein we combine inductive codes into broader categories to define emerging patterns or themes). We will identify and interpret patterns in the data using a thematic analytic approach.

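### Section 9.4.7 reads any significant three-way interaction as suggesting effect heterogeneity, across at least 28 uncorrected tests with low power for modest interactions and no exploratory label

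*Combined protocol and SAP*

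**What the plan says.** All references are to the combined protocol and SAP.

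- **Modifiers (section 9.4.7).** "Secondary endpoints of PLANTS efficacy will be analyzed based on gender, sexual identity, race/ethnicity, intrinsic religiosity, religious attendance, religious activity, and role in school": seven characteristics. Each enters a model with a modifier by arm by time interaction.
- **Reading rule (section 9.4.7).** "A significant 3-way interaction suggests the presence of intervention effect heterogeneity". The next sentence says the team will concentrate on deriving effect sizes and will probe the interaction terms with Stata's margins command.
- **Endpoints (section 3).** Four efficacy endpoints are listed: active-empathic listening, self-efficacy for supporting, affirming and protecting SGMY, and then "Self-efficacy of PLANTS change objectives -Positive bystander intervention behaviors".
- **Scoring of the last one (section 8.1, Staff Baseline Survey).** Two bystander scales are used, "measuring 5 subscales of bystander behaviors each", and the scores to be calculated are subscale averages.
- **Error rate (section 9.4.1).** "All tests are two-tailed", with alpha 0.05. "Given the small sample size and pilot nature of these analyses, we will not perform any corrections for multiple tests".

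The plan gives no power or precision for any interaction. Nothing in section 9.4.7 calls the subgroup analyses exploratory or cautions about false positives.

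**The concern.** Declining to correct for multiplicity is defensible in a pilot as long as p-values are not then used to draw conclusions. Section 9.4.2 keeps to that for the primary endpoints, which are summarised by means and confidence intervals. Section 9.4.7 departs from it for the modifier analyses, because it attaches an interpretation to significance. Applied to a long list of tests, that rule can be expected to yield apparent effect modifiers even when PLANTS works equally well, or equally poorly, for everyone.

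At stake is what the pilot may say about differences in effect by gender, sexual identity, race/ethnicity, religion or role. Section 2.1 says the results will inform a fully powered trial, so a moderation statement made here may be carried forward. The primary endpoints are not affected.

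**Working it through.** **1. The plan's own figures.** There is none for the interactions. The nearest are the confidence interval widths for proportions in section 9.2, from 2 × 1.96 × √(0.25/n):

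- n = 344: 0.106 (stated 0.11)
- n = 172: 0.149 (stated 0.15)
- n = 86: 0.211 (stated 0.21)

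The sample-size chain also reproduces: 4 × 86 = 344 invited, × 0.5 = 172 enrolled, × 0.5 = 86 in PLANTS, × 0.75 = 64.5 completers (stated 65). If EMAILS retention matches, there are about 129 completers in total.

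**2. Number of tests.** 7 modifiers × 4 endpoints = 28, taking one joint test per modifier even where it has several categories. If the ten bystander subscale scores (2 × 5) are analysed separately, the count is 7 × (3 + 10) = 91. The per-protocol population in section 9.3 is defined in the same words as the ITT population, so the planned per-protocol repeat does not double the count as written.

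**3. False positives if no heterogeneity exists.**

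- Expected number in 28 tests: 28 × 0.05 = 1.4. This holds whatever the correlation between tests.
- Chance of at least one, independent tests: 1 − 0.95^28 = 0.762.
- Chance of at least one, correlated tests: the documents give no correlations. A simulation of 28 z-statistics (100,000 draws) with correlation 0.7 among the four endpoints and 0.7 among the three religion measures gives 0.58. With both at 0.5 it gives 0.67.
- At 91 independent tests: 1 − 0.95^91 = 0.991, with 91 × 0.05 = 4.55 expected.

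**4. Power.** The documents give no SD, pre-post correlation (ρ), subgroup prevalence (q) or target interaction. Assumed here: a binary modifier with q between 0.1 and 0.5, ρ between 0.5 and 0.7, 64.5 completers per arm, effects in baseline SD units, and no school-level variation in effects. On pre-post change:

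SE = √(2(1 − ρ)) × √(2 × (1/(64.5q) + 1/(64.5(1 − q))))

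For ρ = 0.5 the first factor is 1. At q = 0.5, SE = √(2 × 2/32.25) = 0.352; at q = 0.1, SE = √(2 × (1/6.45 + 1/58.05)) = 0.587. For ρ = 0.7 the first factor is √0.6 = 0.775, giving 0.273 and 0.455. The effect detectable with 80% power is (1.96 + 0.84) × SE.

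| ρ | q | Power at 0.3 SD | Power at 0.5 SD | Power at 0.8 SD | Detectable at 80% power |
|---|---|---|---|---|---|
| 0.5 | 0.5 | 14% | 29% | 62% | 0.99 SD |
| 0.5 | 0.1 | 8% | 14% | 28% | 1.64 SD |
| 0.7 | 0.5 | 20% | 45% | 84% | 0.76 SD |
| 0.7 | 0.1 | 10% | 20% | 42% | 1.27 SD |

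With only four schools (section 6.3), any school-level variation in effects would lower these figures.

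**5. Share of significant results that are false.** If a proportion π of the tested interactions is real, the share is 0.05(1 − π) / [0.05(1 − π) + power × π]. The documents say nothing about π, so two values are shown:

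- π = 0.10: 0.045/(0.045 + 0.030) = 60% at 30% power; 0.045/(0.045 + 0.010) = 82% at 10% power.
- π = 0.25: 0.0375/(0.0375 + 0.075) = 33% at 30% power; 0.0375/(0.0375 + 0.025) = 60% at 10% power.

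**6. Would correction solve it?** Bonferroni over 28 tests uses 0.05/28 = 0.0018 per test and brings the chance of any false positive to 4.9% (independence). Power at 0.5 SD then falls to about 1% to 10% over the same range of assumptions. Correction alone leaves the tests uninformative.

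**The case against.** The plan is open about not correcting and gives its reason: small sample and pilot purpose. The rule is hedged, since it says *suggests* and not *shows*, and the next sentence turns to effect sizes. These are secondary analyses in a pilot. All of that is true. It makes this a matter of wording and not a flaw in the design, but it does not remove the rule: significance is the only criterion for heterogeneity that section 9.4.7 gives.

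Several stronger readings are tempting, and the documents do not support them:

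- **That only significant interactions will be probed or reported, so real heterogeneity is screened out.** Section 9.4.7 never makes probing conditional on significance. A reader might infer it from the order of the sentences, but it is not written.
- **That the tests have almost no power, or that a significant interaction is more likely noise than signal.** Power is very low for small interactions and small subgroups, but at 0.8 SD in a balanced subgroup it is 62% to 84%. Whether false results outnumber true ones depends on π, as step 5 shows.
- **That the subgroup analyses of the four primary endpoints add 28 more significance tests.** Section 9.4.7 says those differences will be estimated and attaches no significance reading to them.
- **That the per-protocol repeat inflates the count or must be dropped.** As defined in section 9.3 it adds no distinct tests, and whether to keep it is the sponsor's choice.
- **That a false modifier would decide who is offered PLANTS next.** No section proposes targeting by staff characteristics; section 4.2 describes PLANTS as implemented within schools as a whole.

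**Conclusion.** The concern holds in this form: a stated significance rule is applied to at least 28 uncorrected tests without an exploratory label. The expected 1.4 false positives need only the count, the 0.05 level and the absence of true heterogeneity. The 58% to 76% chance of at least one also depends on the assumed correlation between tests, but stays above one half across the range examined. The power figures rest on the assumptions in step 4, none of which the documents supply; over that range the interaction detectable with 80% power is 0.76 to 1.64 SD.

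The two problems are distinct. The number of tests creates the false positives; low power raises the proportion of significant findings that are false and makes a non-significant result uninformative. A reader might conclude that the pilot is bound to publish false effect modifiers. The documents support less than that: followed as written, the rule makes at least one false signal more likely than not if no heterogeneity exists.

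**What to change.** In section 9.4.7, replace the sentence that equates a significant three-way interaction with heterogeneity. The new text should say that:

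- subgroup-specific intervention effects, and the differences between them, will be reported with 95% confidence intervals for every listed modifier and endpoint, whether or not they are significant;
- these analyses are exploratory;
- no claim of effect modification will be based on p<0.05.

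This fits the section's own emphasis on effect sizes and the descriptive approach of section 9.4.2. It needs no new data and no change to the models. The cost is SAP wording, plus the loss to the sponsor of p-value-based statements about moderation.
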